7.2. Reporting Requirements

7.2.1. Adverse Events and Adverse Device Events

Data about relevant AEs or adverse device events are collected through routine data capture (i.e. on the Follow-up Form and through participant reported outcomes on questionnaires). Recurrence of and/or death from breast cancer and the diagnosis of new cancers in participants are outcome

measures of the trial that will be collected via the CRF and are treated as expected events. Further separate collection of adverse event data is not required for trial analysis.

7.2.2. Serious Adverse Events and Serious Adverse Device Events

Whilst it is not anticipated there will be any serious adverse events or serious adverse device events directly related to the study, it is important that this protocol includes a process for dealing with any serious adverse events in the unlikely event they occur. All participants in this study will receive standard NHS treatment. Both types of meshes – biologic matrix and synthetic mesh are used routinely in the NHS. This protocol does not contain investigational agent(s). Therefore, events related to the natural course of the disease and its treatment are expected and not required to be reported as outlined below.

For the purpose of this study, the following are regarded as expected SAEs and should not be recorded as an SAE.

- Haematoma, wound infection, seroma or other surgical complication of breast surgery
- SAEs relating to radiotherapy
- SAEs relating to breast reconstruction
- SAEs relating to adjuvant treatment for breast primary cancer or recurrence
- SAEs relating to lymphoedema events

For the purposes of this study, the following events also constitute expected SAEs and should not be reported to Research ethics.

- Hospitalisations for:
 - Surgical complications related to breast reconstruction, as this information is captured elsewhere in the CRF
 - Pre-planned elective procedures unless the condition worsens.
 - Treatment for progression of the patient's cancer
- Progression or death as a result of the patient's cancer.

For medical devices that are CE marked and being used for their intended use(s) all USADEs must be reported to the REC and the manufacturer.

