7. ADVERSE EVENT MANAGEMENT

7.1. Definitions

Term	Definition		
Adverse Event (AE)	Any untoward medical occurrence, unintended disease or injury, or		
	untoward clinical signs (including abnormal laboratory findings) in		
	subjects, users or other persons, where or not related to the		
	investigational medical device and whether anticipated or		
	unanticipated.		
Adverse Device	An adverse event related to the use of an investigational medical		
Effect (ADE)	device.		
	 NOTE: this definition includes: AEs resulting from insufficient or inadequate instructions for use, deployment, implantation, installation, or operation, or any malfunction of the investigational medical device. Any event resulting from use error or from intentional misuse of the investigational medical device. 'Comparator' if the comparator is a medical device. 		
Serious Adverse	An adverse event that led to any of the following:		
Event (SAE)	• death		
	 serious deterioration in the health of the subject, users, or other persor 		
	as defined by one of more of the following		
	 a life-threatening illness or injury, or 		

	 a permanent impairment of a body structure or a body function including chronic diseases, or in-patient of prolonged hospitalisation, or medical or surgical intervention to prevent life-threatening illness or injury, or permanent impairment to a body structure of a body function, foetal distress, foetal death, a congenital abnormality, or birth defect including physical or mental impairment. NOTE: Planned hospitalisation for a pre-existing condition, or a procedure required by the CIP without a serious deterioration in health, is not considered a SAE.		
Serious Adverse	An adverse device effect that has resulted in any of the consequences		
Device Effect (SADE)	characteristic of a serious adverse event.		
Zerice Litett (JABL)	Situation and a serious duverse events		
Unanticipated	A serious adverse device effect which by its nature, incidence, severity or		
Serious Adverse	outcome has not been identified in the current risk assessment.		
Device Effect			
(USADE)	NOTE: Anticipated serious adverse device effect (ASADE) is an effect which by		
	its nature, incidence, severity or outcome has been identified in the risk assessment.		
Device Deficiency	Inadequacy of a medical device with respect to its identity, quality, durability,		
	reliability, usability, safety or performance.		
	NOTE: This definition includes:		

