7.2.3. Reporting Procedure

Site

Events that meet the criteria for a SAE or SADE per the protocol, should be reported on the SAE form on the Electronic Data Capture (EDC) system by the investigator or a member of the research team. When completing the form, the Investigator will be asked to confirm the following information:

- full details in medical terms and case description
- event duration (start and end dates and times, if applicable)
- action taken
- outcome
- grade of severity
- causality (i.e. relatedness to type of mesh), in the opinion of the investigator
- expectedness

On becoming aware that a patient has experienced a SAE, the Investigator (or delegate) must complete, electronically sign and date the SAE Form on EDC.

Patients should be followed up until resolution or stabilisation of the event. Follow-up information should be provided on a new SAE form.

Trial Office

On receipt of an SAE Form, the Chief Investigator will perform an independent assessment of relatedness. The Chief Investigator will also assess all related SAEs for expectedness. If the event is deemed unexpected (i.e. is not defined as an expected event in Section 7.2.2) it will be classified as an Unexpected and Related SAE.

Reporting to the REC

The Chief Investigator/Trial co-ordinator will report all events that are categorised as Unexpected and Related SAEs to the REC within 15 days of receipt. Details of all Unexpected and Related SAEs and USADEs will also be reported to Principal Investigators at recruiting sites.

All related and unexpected SAEs must be reported by the investigator using the 'non-CTIMP safety report to REC form' from the HRA website. The completed form should be submitted to the Sponsor and REC within 15 days of the CI becoming aware of the event. Safety information will be reviewed during trial management group meetings.

UHDB contact information:

Email: [contact]

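### Serious mesh-related events face two different expectedness tests, and the SAE window closes before the 6-month post-surgery assessment

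*Protocol*

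**What the plan says.** **Expectedness.** Section 7.1 of the protocol defines a USADE as a serious device effect which, by its nature, frequency, severity or result, lies outside what was foreseen: its "outcome has not been identified in the current risk assessment". Section 7.2.2 then gives a list of event types with the instruction "For the purpose of this study, the following are regarded as expected SAEs and should not be recorded as an SAE". One entry is "SAEs relating to breast reconstruction", and another takes in any other surgical complication of breast surgery. A second list says that hospital admissions for complications of the reconstruction need not go to the ethics committee. The section closes by requiring, for CE-marked devices in their intended use, that "all USADEs must be reported to the REC and the manufacturer".

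Section 7.2.3 tells sites: "Events that meet the criteria for a SAE or SADE per the protocol, should be reported on the SAE form". That form asks for "causality (i.e. relatedness to type of mesh), in the opinion of the investigator" and for expectedness. The Chief Investigator then applies a list-based test: "If the event is deemed unexpected (i.e. is not defined as an expected event in Section 7.2.2"), it becomes an Unexpected and Related SAE. The reporting deadline covers events "categorised as Unexpected and Related SAEs to the REC within 15 days of receipt".

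**Window.** Section 7.2.4 has related SAEs, other than those on the 7.2.2 list, reported from randomisation until 6 months after randomisation. Related SAEs found later go to the Trial Office. Section 6.5.1 schedules complications and questionnaires at 3 and 6 months after surgery. Section 6.3 places randomisation before surgery, with enough days left to order the mesh.

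**The concern.** Section 7.1 measures a serious mesh event against the risk assessment. Sections 7.2.2 and 7.2.3 measure it against a fixed list that has no limit on severity or frequency. The mesh is implanted as part of the reconstruction, so a serious mesh event falls naturally under the reconstruction entry. The same event can then be unanticipated under one rule and expected, and not recorded as an SAE, under the other.

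The SAE form is the only place the protocol describes for judging whether a serious event is related to the type of mesh and whether it was expected. A site that applies the list literally completes no form, so that assessment and the Chief Investigator's review of it are not triggered. What is at stake is causality assessment and expedited reporting of an unanticipated device effect, in a trial whose own rationale is uncertainty about mesh safety.

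The second problem is that two clocks start at different points. The SAE clock starts at randomisation and the follow-up clock at surgery, and both run for 6 months.

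**Working it through.** **Part 1: the rules side by side.** The protocol states no figure on this point, so there is none to reproduce. Take a serious event caused by the mesh, arising from the reconstruction, and more severe than the risk assessment foresaw.

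| Rule | Reference used | Result for this event |
|---|---|---|
| 7.1, USADE definition | Risk assessment, including severity | Unanticipated: a USADE |
| 7.2.2, closing sentence | USADE status | Report to ethics committee and manufacturer |
| 7.2.2, first list | Event type only | Expected; not recorded as an SAE |
| 7.2.2, second list (if admitted to hospital) | Event type only | Not reported to the ethics committee |
| 7.2.3, Chief Investigator's test | The 7.2.2 list | Cannot be unexpected |
| 7.2.3, 15-day rule | Unexpected and Related label | Does not attach |
| 7.2.4, documentation duty | The 7.2.2 list | Excluded, with no exception for USADEs |

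The second row conflicts with the third and fourth, and no sentence ranks them. Even if the USADE duty is taken to prevail, the only stated deadline depends on a label that a listed event cannot receive. The duty then has no stated time limit.

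**Part 2: the window.** The inputs are an SAE window of 6 months from randomisation (7.2.4), follow-up of 6 months from surgery (6.5.1), and randomisation before surgery (6.3). The length of the gap between them is not given, so it is assumed here. With 6 months taken as 26 weeks and a gap of *g* weeks:

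- post-surgery weeks inside the window = 26 − *g*
- share of post-surgery follow-up outside it = *g* / 26

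| Assumed gap (weeks) | Weeks inside | Share outside |
|---|---|---|
| 1 | 26 − 1 = 25 | 1/26 = 3.8% |
| 2 | 26 − 2 = 24 | 2/26 = 7.7% |
| 4 | 26 − 4 = 22 | 4/26 = 15.4% |
| 8 | 26 − 8 = 18 | 8/26 = 30.8% |

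For any gap above zero, a 6-month assessment held on schedule falls after the window has closed. If the window ended 6 months after surgery, the uncovered time before that assessment would be zero.

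**The case against.** The strongest reply is that SAE and USADE are separate categories with separate tests. Section 7.2.3 names them separately when it says what principal investigators at the sites will be told. The USADE sentence comes after both lists, is specific to devices and has no exceptions, so it can be read as prevailing. A USADE is by definition a serious adverse device effect (SADE), and 7.2.3 asks for the form for an SAE or SADE. The list also has a stated reason: both meshes are routine care and surgical complications are captured elsewhere on the case report form. Section 11.2 binds the trial to the Sponsor's procedures, which are not shown and might set a USADE deadline.

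That reading is possible, but the text does not settle it. The form is required for events that qualify under the protocol, and the protocol says listed events are not recorded as SAEs. Section 7.2.4 repeats the exclusion and makes no exception for USADEs.

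On the window, late related SAEs still go to the Trial Office, and the principal investigator must check for SAEs and SADEs whenever participants attend follow-up. This softens the mismatch without removing it. Follow-up may be by telephone or from records, and the late-event clause acts only on events that happen to be identified. It is also fair that the 8-week case has no support in the text; it is there only to show a range.

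What stands from the objection is a limit on the consequences. Complications are still collected to 6 months after surgery and summarised by treatment received (6.5.1, 9.2). The Trial Management Group reviews safety information, and an independent Trial Steering Committee oversees the trial.

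**Conclusion.** Both parts hold. The protocol applies two expectedness standards to serious mesh-related events without saying which governs. A USADE that falls on the 7.2.2 list has a reporting duty but no deadline in the protocol. The SAE window also ends before the 6-month post-surgery assessment, by exactly the randomisation-to-surgery gap. For assumed gaps of 1 to 8 weeks that is 4% to 31% of post-surgery follow-up. These percentages describe time outside the defined window, not a share of events lost. The protocol gives no expected number of unanticipated device effects, and none is claimed.

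No feasibility outcome, progression criterion or complication count changes. The weakness is confined to mesh causality and expectedness assessment and to expedited reporting. It should be corrected, but it does not threaten the trial's main conclusions. Confidence is medium, because a reading that favours the USADE sentence is available.

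**What to change.** - Reconcile Sections 7.1, 7.2.2 and 7.2.3 so that device-related serious events are judged for expectedness by one standard.
- State in 7.2.2 that the list does not override the USADE rule, and carry the same exception into 7.2.4.
- State in 7.2.3 that a possible USADE goes on the SAE form even when its event type is listed, and which reporting deadline applies to it.
- Reconcile the 7.2.4 window with the schedule in 6.5.1 so that it covers the 6-month post-surgery assessment.

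The cost is wording in Sections 7.2.2 to 7.2.4 and a few more SAE forms. Routine complications can stay on the follow-up form as now.

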7.2.3. Reporting Procedure

Site

Events that meet the criteria for a SAE or SADE per the protocol, should be reported on the SAE form on the Electronic Data Capture (EDC) system by the investigator or a member of the research team. When completing the form, the Investigator will be asked to confirm the following information:

- full details in medical terms and case description
- event duration (start and end dates and times, if applicable)
- action taken
- outcome
- grade of severity
- causality (i.e. relatedness to type of mesh), in the opinion of the investigator
- expectedness

On becoming aware that a patient has experienced a SAE, the Investigator (or delegate) must complete, electronically sign and date the SAE Form on EDC.

Patients should be followed up until resolution or stabilisation of the event. Follow-up information should be provided on a new SAE form.

Trial Office

On receipt of an SAE Form, the Chief Investigator will perform an independent assessment of relatedness. The Chief Investigator will also assess all related SAEs for expectedness. If the event is deemed unexpected (i.e. is not defined as an expected event in Section 7.2.2) it will be classified as an Unexpected and Related SAE.

Reporting to the REC

The Chief Investigator/Trial co-ordinator will report all events that are categorised as Unexpected and Related SAEs to the REC within 15 days of receipt. Details of all Unexpected and Related SAEs and USADEs will also be reported to Principal Investigators at recruiting sites.

All related and unexpected SAEs must be reported by the investigator using the 'non-CTIMP safety report to REC form' from the HRA website. The completed form should be submitted to the Sponsor and REC within 15 days of the CI becoming aware of the event. Safety information will be reviewed during trial management group meetings.

UHDB contact information:

Email: [contact]

7.2.4. Reporting Period

The PI is responsible for checking for SAEs and SADEs when participants attend for treatment and follow-up. Details of all related SAEs (except those listed in Section 7.2.2) will be documented and reported from randomisation until 6 months post randomisation. This reporting period should be sufficient to capture all SAEs associated with the trial protocol however, if a related SAE is identified after this period, the event should be reported to the Trial Office.

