9.2. Statistical Analysis

Descriptive statistics will be presented to summarize the distribution of demographic and baseline variables across each of the randomisation groups. A Consolidated Standards of Reporting Trials (CONSORT) flow diagram will be produced, showing the frequency of patients/ participants:

- · Assessed for eligibility and reasons for not eligible,
- · Approached and reasons for not approached
- · Confirmed as eligible
- Consented and reasons for not consented
- Excluded before randomisation (and the frequency of each reason for exclusion),
- Randomised,
- · Allocated to each randomisation group,
- That received each allocated type of mesh,
- That did not receive each allocated type of mesh,
- Lost to follow-up (and the frequency of each reason for loss to follow-up) for each randomisation group.
- Analysed for each randomisation group.
- Not analysed (and the frequency of each reason for not being analysed) for each randomisation group.

Primary analysis will be intention-to-treat. Clinician acceptance (proportion of eligible women offered the trial), patient acceptance (proportion of women offered the trial who participate in the trial), randomisation rate and recruitment rate (average per year) will be presented overall as proportions along with 95% confidence intervals. Compliance with allocated type of mesh and completeness of data (primary and secondary endpoints) will be presented overall and by study group using summary statistics along with 95% confidence intervals.

Secondary outcome measures will be presented overall and by study groups, as summary statistics at each assessment point. The standard deviation and effect size of Breast Q will be estimated using an Independent T-Test. Safety outcomes (AEs, SAEs, complications) will be presented with summary statistics by the treatment that has been received.

Missing data will be excluded from analysis and will not be imputed.

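### Sections 7.2.3 and 7.2.4 are inconsistent on whether sites report all SAEs outside the 7.2.2 list or only those they judge related

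*Protocol*

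**What the plan says.** Section 7.2.3 (Reporting Procedure) sets the site's duty: "Events that meet the criteria for a SAE or SADE per the protocol, should be reported on the SAE form". The trigger is awareness of the event, not an opinion on its cause: "On becoming aware that a patient has experienced a SAE, the Investigator (or delegate) must complete, electronically sign and date the SAE Form". Among the items on the form is "causality (i.e. relatedness to type of mesh), in the opinion of the investigator". The next step is "On receipt of an SAE Form, the Chief Investigator will perform an independent assessment of relatedness", followed by "The Chief Investigator will also assess all related SAEs for expectedness".

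Section 7.2.4 (Reporting Period) describes the duty differently: "Details of all related SAEs (except those listed in Section 7.2.2) will be documented and reported". The period runs from randomisation to 6 months after randomisation. A further sentence sends any related SAE found later to the Trial Office.

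Section 7.2.2 lists expected events that are not to be recorded as SAEs, including surgical complications of breast surgery and SAEs relating to breast reconstruction. The assessment table in 6.5.1 places follow-up at months 3 and 6 after surgery. Section 9.2 states the use of the data: "Safety outcomes (AEs, SAEs, complications) will be presented with summary statistics by the treatment that has been received".

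**The concern.** Section 7.2.3 treats relatedness as something recorded after the decision to report. Section 7.2.4 can be read as making it a condition for reporting at all. A site that takes 7.2.4 as its rule would decide causality first and submit nothing for an SAE it considers unrelated.

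Two things are at stake. The first is the Chief Investigator's review. It exists to check the site's opinion, but it could then only confirm or downgrade events the site had already called related. The protocol has no DMEC, so this review is the main named check on site causality. The second is the SAE summary in 9.2. With five planned sites, the counts may reflect which section each site followed as well as what happened to the patients.

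A separate mismatch sits in the same sentence of 7.2.4: the reporting clock starts at randomisation, whereas follow-up is timed from surgery.

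**Working it through.** The protocol states no figure that can be reproduced here. The check sets the sections side by side.

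**Which events are reported**

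1. *Definition (7.1).* An SAE is an adverse event with a serious consequence, and an adverse event counts whether or not it is related to the device. Relatedness enters only with the device-effect categories (ADE, SADE, USADE).
2. *Exclusions (7.2.2).* Listed events are removed by type. The list contains no general rule that unrelated SAEs go unreported.
3. *Set A (7.2.3 read with 7.2.2).* All SAEs outside the list, related or not. Section 7.2.3 refers to criteria set by the protocol, so it is already limited by 7.2.2.
4. *Set B (7.2.4 read as a limit).* SAEs outside the list that the site judges related.
5. *Difference, A minus B.* Every SAE outside the list that the site judges unrelated.

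**Which reading the review process needs**

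The Chief Investigator assesses relatedness for each form received, and then expectedness for the related ones only. The narrowing between those steps implies that forms for unrelated SAEs are expected to arrive. Set A supplies them; set B does not.

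**Whether 7.2.4 concerns only timing or REC reporting**

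Its heading refers to the period. Its text, however, covers documentation as well as reporting, places the duty to check for SAEs on the site's PI, and names the Trial Office as recipient of late events. REC reporting has its own paragraphs in 7.2.3. Section 7.2.4 is therefore at least open to being read as a rule on what sites submit.

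**The reporting period**

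Let *d* be the time from randomisation to surgery, in months.

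- Post-operative time inside the 7.2.4 period = 6 − *d*.
- Post-operative follow-up in 6.5.1 = 6.
- Shortfall = 6 − (6 − *d*) = *d*.

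Section 6.3 requires randomisation early enough before surgery to order the allocated mesh, so *d* > 0 and the period closes before the month-6 post-surgery time point. The protocol gives no value for *d* and speaks only of days for ordering, so the shortfall may be short. After the period closes, the late-event sentence covers related SAEs only.

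**The case against.** The strongest defence is that 7.2.4 requires related SAEs to be reported but does not say that only these are. Section 7.2.3 is the procedure section and carries the mandatory wording. A reader might infer that sites cannot comply with both sections. The text does not support that: a site filing a form for every SAE outside the 7.2.2 list satisfies both. What remains is an ambiguity, in that 7.2.4 can be read as narrowing 7.2.3 and nothing says which governs.

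A reader might also infer a biased safety comparison between meshes, because only participants are described as blinded and causality is defined by mesh type. That goes too far. Under either section, 7.2.2 removes surgical complications and reconstruction-related SAEs from SAE recording. Infection, implant loss, reoperation, readmission and the other listed complications are collected at 3 and 6 months after surgery with no relatedness filter, and 9.2 names complications separately from SAEs.

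Nor do the documents show that an unexpected device effect would go unseen. Section 7.2.2 separately requires all USADEs to go to the REC and the manufacturer. That duty still depends on someone recognising the event as device-related, so it reduces the gap without closing it.

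On the period, related SAEs found late still go to the Trial Office, so what falls outside is unrelated non-listed SAEs. Finally, SAEs are not a primary or secondary outcome (3.2) or a progression criterion (9.4). These points limit the size of the problem, but they do not reconcile the two sections.

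**Conclusion.** The inconsistency is real and minor. If 7.2.4 is taken as a limit, non-listed SAEs that the site judges unrelated are not submitted, the Chief Investigator cannot upgrade a site's judgement, and the SAE counts in 9.2 may not be comparable between sites. The reporting period also ends before the month-6 post-surgery visit, by the interval between randomisation and surgery.

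The effect is confined to what should be a small number of events in a trial of 60 women. The protocol gives no SAE rate, no expected share judged related and no waiting time to surgery, so no percentage of lost events can be put on it. No feasibility conclusion changes. The conclusion rests on one assumption: that at least one site could reasonably read 7.2.4 as restricting what it reports.

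**What to change.** Reconcile 7.2.3 and 7.2.4 into one rule on which SAEs sites enter on the EDC form. Stating a related-only limit consistently in both sections would also remove the contradiction, but it would leave the Chief Investigator's independent relatedness review unable to do its job. To keep that review workable:

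- In 7.2.4, refer to all SAEs other than those 7.2.2 says not to record, whatever the site's view of relatedness.
- State that relatedness and expectedness decide only onward reporting to the REC.
- Run the reporting period from randomisation to the month-6 post-surgery follow-up, and keep the sentence on later related SAEs.

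The cost is a protocol wording amendment and a few more SAE forms.
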